**MRI Scanning**

The collection of MRI images will take place in a 3T magnet scanner with multi-channel receivers. All protocols have been developed and validated at the Martinos Center for biomedical imaging.

Participants will undergo conventional high-resolution 3D T1-weighted MPRAGE scans, resting state functional connectivity MRI sequences, and task-based functional connectivity MRI sequences.

We will examine areas pertaining to impulsivity, mood, and executive function, including but not limited to the Salience Network, Central Executive Network, Limbic Areas, Default Mode Network, and the dlPFC.

This data will be used to test the effect of a single t-PBM session on cerebral blood flow (CBF), while irradiating R-dlPFC (SA1), in subjects with impulsivity due to BD and to test the effect of repeated t-PBM sessions on CBF (SA2).

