Mechanistically, t-PBM with NIR (wavelength 800–1100 nm) is absorbed by the cytochrome C oxidase (CCO) in neuronal mitochondria, leading to an increased synthesis of adenosine triphosphate (ATP), along with photodissociation of nitric oxide (NO) and cerebral vasodilation and subsequent increase in cerebral blood flow (CBF). t-PBM increases cerebral blood flow (CBF) based on SPECT, Doppler Ultrasound, and fNIRS reports. This proposal will use the fMRI BOLD signal as the biomarker of CBF change induced by t-PBM. The BOLD signal was previously validated as a marker of target engagement and as a predictor of treatment outcome in other NIBs. t-PBM to the R-dlPFC led to both increase of BOLD signal and to cognitive improvement in adults with cognitive deficits. ***By engaging the CBF (BOLD), we will test the propensity of t-PBM to modulate R-dlPFC in patients with impulsivity due to bipolar disorder.***

At MGH, we are conducting a single-blind, sham-controlled (paired sample) study to test the effect of bilateral t-PBM on fMRI BOLD signal (dlPFC) in adults (n=15) with major depressive disorder. We have demonstrated feasibility for multiple t-PBM sessions per week and for the delivery of t-PBM within MRI scanner, while recording BOLD signal (NCT04366258). A collaboration between MGH and colleagues in Italy piloted bilateral t-PBM in adults (n=4) with BD. t-PBM was helpful in alleviating BD residuals, including impulsivity and irritability.

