## 2. Specific Aims and Objectives

**1. To test the effect of a single t-PBM session on cerebral blood flow (CBF), while irradiating R-dlPFC, in subjects with impulsivity due to BD**

*Hypothesis:* a single t-PBM session on the R-dlPFC will significantly increase BOLD-signal at the R-dlPFC, relative to sham.

**2. To test the effect of repeated t-PBM sessions on CBF, after irradiating R-dlPFC, in subjects with impulsivity due to BD**

*Hypothesis:* repeated t-PBM sessions on the R-dlPFC will significantly increase BOLD-signal at the R-dlPFC at day 5 relative to baseline.

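### Aims 1 and 2 are framed as effects on cerebral blood flow, but only BOLD is measured, and the plan does not say what a null or negative BOLD result means for flow.

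*Combined protocol and SAP*

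**What the plan says.** Section 2 words Aim 1 as follows: "To test the effect of a single t-PBM session on cerebral blood flow (CBF), while irradiating R-dlPFC". Aim 2 is likewise titled as an effect on flow. Section 3 calls the effect on flow the primary aim, and section 7 says the team will stress that the study examines the impact of t-PBM on flow. Section 6 (MRI Scanning) says of the images: "This data will be used to test the effect of a single t-PBM session on cerebral blood flow (CBF), while irradiating R-dlPFC (SA1", and continues in the same way for Aim 2. Section 1 describes flow itself as the most reliable biomarker of engaging the target.

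The hypotheses are about a different quantity. For Aim 1: "a single t-PBM session on the R-dlPFC will significantly increase BOLD-signal at the R-dlPFC, relative to sham". For Aim 2: "repeated t-PBM sessions on the R-dlPFC will significantly increase BOLD-signal at the R-dlPFC at day 5 relative to baseline". The images acquired are these: "Participants will undergo conventional high-resolution 3D T1-weighted MPRAGE scans, resting state functional connectivity MRI sequences, and task-based functional connectivity MRI sequences". The scan orders given for Treatments 1 and 5 add nothing that measures perfusion. Section 9 names BOLD percent signal change over the region of interest as the dependent variable.

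Section 1 declares the link between the two: "This proposal will use the fMRI BOLD signal as the biomarker of CBF change induced by t-PBM". Its support is: "The BOLD signal was previously validated as a marker of target engagement and as a predictor of treatment outcome in other NIBs". For mechanism, it says that light is absorbed by cytochrome C oxidase, "leading to an increased synthesis of adenosine triphosphate (ATP), along with photodissociation of nitric oxide (NO) and cerebral vasodilation", followed by increased flow.

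**The concern.** The primary aim names a quantity that the trial does not measure. A declared surrogate can be acceptable, but the stated validation concerns target engagement and outcome prediction with other devices. It is neither agreement with measured flow nor evidence under t-PBM.

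This matters because BOLD reflects the balance of oxygen delivery and oxygen use. It follows flow closely only when oxygen use changes little. An intervention said to raise ATP synthesis may also raise oxygen use, which would pull BOLD down for a given rise in flow.

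What is at stake is mainly a null or negative result. Nothing in the plan prevents it from being reported as no effect on flow or as failure to engage the target. The power statement rests on a one-tailed test, so a fall in BOLD would simply appear as non-significant.

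**Working it through.** **Aim against measurement**

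| Item | Quantity | Place |
|---|---|---|
| Titles of Aims 1 and 2 | Flow | Section 2 |
| Primary-aim sentence | Flow | Section 3 |
| Stated use of the MRI data | Flow | Section 6, MRI Scanning |
| Study purpose to be emphasised | Flow | Section 7 |
| Hypotheses 1 and 2 | BOLD | Section 2 |
| Sequences | T1, resting-state and task functional MRI | Section 6 |
| Dependent variable | BOLD percent signal change | Section 9 |

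No section limits the conclusion to BOLD.

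**How far BOLD and flow could separate**

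The plan has no figure on this, so there is none to reproduce. The 80% power in section 9 concerns the BOLD contrast and is not used here. The following is an illustration with a calibrated-BOLD model:

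BOLD change = M × [1 − f^(α−β) × r^β]

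Here f is relative flow and r is relative oxygen use. All constants are assumptions from outside the documents: M = 8%, and (α, β) = (0.38, 1.5) or (0.2, 1.3). Flow is set to rise 10%, so f = 1.10.

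- Flow factor: 1.10^(−1.12) = 0.89875; 1.10^(−1.1) = 0.90047.
- Oxygen use unchanged (r = 1): 8% × (1 − 0.89875) = +0.81%; 8% × (1 − 0.90047) = +0.80%.
- Oxygen use up 5%: 1.05^1.5 = 1.07593, so 8% × (1 − 0.89875 × 1.07593) = +0.26%; 1.05^1.3 = 1.06548, so 8% × (1 − 0.90047 × 1.06548) = +0.32%.
- Oxygen use up 10%: the bracket becomes 1 − 1.10^α, giving −0.30% and −0.15%.
- BOLD is zero when r = f^((β−α)/β): 1.10^0.7467 = 1.074 and 1.10^0.8462 = 1.084.

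At a 5% rise in oxygen use, the BOLD signal for the same flow increase shrinks by 1 − 0.264/0.810 = 67% or 1 − 0.325/0.796 = 59%. BOLD vanishes when oxygen use rises about 74% to 84% as much as flow (7.4/10 and 8.4/10). Over a wider assumed grid (α from 0.2 to 0.38, β from 1.0 to 1.5), the zero point for a 10% flow rise lies between +6.1% and +8.6% oxygen use.

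**What a positive result supports**

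BOLD is positive only if r < f^((β−α)/β). If oxygen use does not fall (r ≥ 1), this requires f > 1. So in this model a positive contrast does indicate a rise in flow. It does not give the size: about +0.3% BOLD arises from a 10% flow rise with oxygen use up 5%, and also from a smaller flow rise with oxygen use unchanged.

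**The case against.** The surrogate is not hidden. Section 1 names BOLD as the biomarker, and the hypotheses, dependent variable and power statement are all in BOLD, so the tests match the data. No reporting rule says that conclusions will be drawn about flow; that is read from the titles and purpose sentences. This stands, and it makes the problem one of framing and interpretation, not of a mismatched test.

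A reader might go further and infer that the protocol's own mechanism makes BOLD flat or falling while flow rises, so that Aims 1 and 2 cannot be answered. The documents do not support that:

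- Section 1 speaks of ATP synthesis, not of raised oxygen use. Oxidative metabolism appears only in the title of reference 45.
- Section 1 also gives a vasodilatory route through nitric oxide. If that raises flow beyond metabolic demand, BOLD rises.
- The cited human evidence is of increases: section 1 reports higher BOLD with R-dlPFC treatment, and section 9 reports an increase as high as 31% in dlPFC.
- A flat BOLD needs a large metabolic rise relative to flow, and no figure in the documents shows that this applies.

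The illustrated percentages are also not anchored to the protocol. With M = 8% the model cannot exceed +8%, well below the 31% cited. The zero point and the proportional attenuation do not depend on M, but they do depend on α and β.

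It would likewise be excessive to require a positive result to be reported as a BOLD change with no bearing on flow, since a positive contrast implies a flow rise unless oxygen use falls.

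**Conclusion.** The concern holds as a gap between the named target and the measured one. Four places in the plan frame the main imaging question as flow. Only BOLD is acquired, and the stated support for the substitution is not agreement with measured flow.

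The practical consequence is one-sided. A null or negative BOLD contrast would not exclude a flow increase. A positive one would be consistent with increased flow, without quantifying it.

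The illustrated size is a loss of about 59% to 67% of the BOLD signal if oxygen use rises half as much as flow, and complete loss at about 74% to 84%. These figures rest on assumed constants and on the inference that t-PBM raises oxygen use. They show that a real flow effect could be attenuated or missed, not that it will be.

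**What to change.** - Reword Aims 1 and 2 as the effect of t-PBM on R-dlPFC BOLD signal, described as an indirect surrogate for flow.
- Make the matching change in section 1 (flow as the most reliable biomarker), section 3 (primary aim), section 6 (MRI Scanning, Aims 1 and 2) and section 7 (study purpose).
- Add an interpretation rule to section 9. A null or negative BOLD contrast will not be concluded as no change in flow or no target engagement. A positive contrast will be reported as a BOLD increase consistent with increased flow, with no claim about the size of the flow change.

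This needs no new scan and no change to the sample size, visits or test. The cost is a wording change and a narrower claim.

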## 7. Risks and Discomforts

*Screening and Evaluation:* The risks and discomforts of the screening evaluations include discomfort or distress responding to potentially sensitive questions regarding mental illness and drug use. Research interviews are interrupted if individuals become distressed or object to answering questions.

*Delay in Initiation of New, or Changes in Ongoing, Bipolar Treatment:* While this study is not testing t-PBM as a treatment for bipolar disorder, it is possible that participants will experience improvements to their symptoms while undergoing t-PBM. Any delay in receiving t-PBM (while screening procedures are completed) might be considered as a delay in treatment from a patient perspective. We will emphasize that the study is not geared to test a treatment but instead the impact of t-PBM on cerebral blood flow.

Further, study participation requires stable BD treatment during and two-weeks prior to enrollment. Subjects should not change medications, treatments, or therapeutic interventions two weeks prior to study enrollment or during study participation as to avoid interference with t-PBM treatment. However, without adjustment of medication it is possible that participants' symptoms may worsen while participating in the study. This may include increased disturbances in mood, anxiety, sleep, appetite, energy, or cognition. This could result in work loss, loss of social function, and possibly increased risk of suicide. Therefore, there is some risk to halting medication changes while in the study. However, the risk will be minimized as there are several safety precautions in place and participants will have frequent contact with study clinicians. The clinical monitoring in this study exceeds that of standard care for BD. The potential benefits of improving impulsivity and cognition offset the risk of worsening BD symptoms.

*Risks of Clinical Decompensation:* If a patient has worsened to such a degree that further participation would put them at risk, then they will be discontinued from the study. In such cases, the patient is immediately transferred to standard clinical treatment and exited from the research.

At any point during the study, patients are told to immediately inform their study psychiatrist if they develop worsening of depression or anxiety, symptoms of mania or psychosis, or active suicidal plans.

*Suicidality Standard Operating Plan (SOP):* If a subject spontaneously expresses suicidal ideation and the thoughts are passive, vague, or infrequent, the study team will respond with close monitoring of the subject. This may include phone calls, video calls, or in-person check-ins between the study clinician and the subject. If the suicidal ideation includes more specific thoughts, intent, and/or plans, if the subject responds “Yes” to questions 4 or 5 of the C-SSRS, or if the subject answers 1, 2, or 3 to Question 9 of the PHQ-9, then they will be proactively discontinued from the study and referred to adequate care.

*Risks associated with study tasks:* Performing tasks can result in frustration related to difficulty with performance, or boredom during longer sittings. Participants may refuse to answer questions that make them uncomfortable.

*Risks of Magnetic Resonance Imaging:* MRIs use powerful magnets to make images. There are no known radiation risks associated with MRI. However, individuals with metal implants, such as surgical clips or pacemakers, should not have an MRI. All credit cards and other items with magnetic strips should also be kept out of the MRI room. People who feel uncomfortable in confined spaces (claustrophobia) may feel uncomfortable in the narrow tube. The MRI makes loud banging noises as it takes images. Earplugs can be used to reduce the noises. The MRI can be stopped at any time at subject’s request. If the study subject is or suspects they are pregnant, they should not participate in this study. Study staff will assess chance of pregnancy. If there is any uncertainty, a study physician can recommend a pregnancy test. The MRI has the potential, during normal routine use, to cause localized warming of participant’s skin and of the underlying tissues. The participant will be instructed to immediately inform study staff if they experience discomfort due to warming and the procedure will be stopped.

Some people experience dizziness or rarely nausea when going into an MRI scanner and these sensations may be more common in scans with higher magnetic fields. In most cases, these symptoms only last a short time. However, some people may experience them throughout the scan and/or continue to experience them for a short period of time after (generally, less than half an hour). No case of permanent problems is known.

*Risks of tPBM:* The study laser device emits light with a longer wavelength than the human eye can see. The staff will be provided training on basic safety procedures relative to the use of the device. The staff administering the t-PBM will be careful not to operate the laser unless it is in direct contact with the subject’s skin. Protective eyewear is required since the device is a laser. Failure of laser device, resulting in the cessation of investigative therapy can cause no adverse event to our knowledge. Delivery of the infrared laser energy to an inappropriate site, such as directly over the open eye, would pose risk to the subject, such as blindness. Based on previous observations with similar laser devices, application of the laser may result in mild thermal sensation of warmth during use. The temperature of the skin is however kept well below the level for thermal damage. Based on human clinical trial experience to date and on sale of t-PBM devices for their intended use (e.g. Omnilux New-U), each adverse event listed below has been

reported by less than 0.1% of all subjects and users: erythema, pain, discomfort, warmth, headache, or other reactions at the application site. In our research experience, t-PBM devices could produce insomnia, irritability, and fleeting illusions. The modality of administration for t-PBM with the study laser device is analogous to the protocols used in our feasibility studies. The dose of light delivered by the study device is analogous to our feasibility studies and to published studies on t-PBM. No serious adverse events occurred during our feasibility trials.

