Treatment 5 should ideally occur the day after Treatment 4. If necessary, this window can be extended so that this visit occurs within ten days of the Treatment 1 visit (in this case, the timing of follow up visits will be adjusted accordingly). Adverse events, concomitant medications and therapies, and vitals will be assessed and recorded. The MRI Safety Checklist will be completed and signed before the MRI. Participants will complete the MOODS-SR, the BIS, the BRIEF-A, and the I-7.

Participants will undergo an MRI Scan. A structural scan and a pre-stimulation resting state functional scan will be collected first. Active t-PBM will be administered immediately after the resting-state scan, followed by a post-stimulation resting state functional scan. Participants will then complete the Delgado gambling task. A functional sequence will be collected during the gambling task administration. The MRI will last approximately 45 minutes in total.

Participants will complete the SAFTEE, the CAST-IRR, the TSRQ, and the Iowa gambling task after the MRI/t-PBM session. Study staff will complete an intervention tracking form.

*Clinical Check-in Call*

A licensed study clinician will call the participant (phone or video call) approximately 2-3 days after the final treatment session. Adverse events and concomitant medications and therapies will be assessed and recorded. The clinician will administer the C-SSRS and the CGI-S/I. The clinician may use the PHQ-9 and/or ASRM to guide their call with the study participant, though these scales do not need to be completed in full. The purpose of this call is to check in on the general safety and well-being of the participant.

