## Assessments

### *Adverse Events Form*

The Adverse Events Form captures any adverse event (serious or otherwise) that the subject experiences while participating in the study. Events may occur during or outside of study procedures.

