## **10. Monitoring and Quality Assurance**

At enrollment, each subject will be assigned a unique ID number that will be used in place of a subject's name across all study forms and documents. Documents will be stored separately from other materials in a locked filing cabinet that is only accessible by study staff. Subjects may request that their data be withdrawn by contacting [name] (contact information provided on the consent form). Experienced, doctoral-level clinicians will be available to participants by phone, or in-person if necessary, to discuss any concerns throughout the study. This will be clearly communicated orally and in writing to subjects.

The data gathered from the project will include imaging and treatment data. Information relating to the data derived from this study will be made available to Partners IRB. The information collected in the study will be used only for research purposes. There are no plans to share any of the collected data with anyone outside of the immediate study staff.

[name], PhD (Neuropsychiatry), Director of Photobiomodulation at MGH Depression Program and at MGH Neuropsychiatry will provide his expertise on t-PBM and its effects on psychiatric conditions. [name], MPH is Chief of the Division of Neuropsychiatry at MGH and directs the Laboratory of Neuropsychiatry and Neuromodulation. His will provide his expertise in imaging studies of neuromodulation. [name] Is the director of Dimensional Neuroimaging Research within the Division of Neuropsychiatry and will provide her expertise in bipolar disorder and neuroimaging. [name], [name], and [name] all have extensive clinical research and data safety monitoring experience. [name], as the principal investigator, will discuss safety concerns with research study team (CRCs and post-doc) and bring any concerns to the other co-Is, if needed. [name] will provide safety monitoring and insight for neuroimaging and [name] will provide her insight for safety of bipolar disorder subjects. In addition to these internal monitors, [name], MSc., will serve as the independent monitor for the study. He is the Director of Clinical Research at the Nathan Kline Institute in New York and has extensive experience within the field of Psychiatry and t-PBM as a PI and co-I of many studies within the field. He will review the annual reports for safety, and findings, and he will provide feedback on the study.

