Expected adverse events and expected serious adverse events will not be accepted by the Mass General IRB nor will they be reported unless the sponsor or investigator deems the event to be unexpected in nature. Only Unanticipated Problem Involving Risks to Subjects or Others (UPIRTSO) and Unanticipated Adverse Device Effect (UADE) Events meeting either of these definitions are considered "Unanticipated Problems" and should be reported if they occur during the conduct of the study, after study completion, or after subject withdrawal or completion. Events meeting these definitions include unexpected or unanticipated drug or device adverse reactions attributable to the intervention and that place subjects at increased risk of harm.

In the case of an unexpected adverse event and in accordance with Partners Human Research Committee Adverse Event Reporting guidelines, the PI and study staff will complete the appropriate adverse event form and send it to the IRB within the required time frame for reporting. This documentation will be completed and submitted on Insight within 5 business/7

calendar days from the day the investigator first became aware of the event. This report will include:

- a detailed description of the event
- the basis for determining that the event is unexpected in nature, severity, or frequency
- the basis for determining that the event is related or possibly related to the research procedures
- the basis for determining that the research places subjects at an increased risk of harm)
- whether any changes to the research or other corrective actions are warranted.

Experienced, doctoral-level clinicians will be available to participants by phone, or in-person if necessary, to discuss any concerns throughout the study. This will be clearly communicated orally and in writing to subjects.

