All monitoring and quality assurance procedures will be in accordance with the MGH sub-committee on human studies. The PI will oversee the collection, maintenance, and analysis of the data. Research affairs will be contacted immediately in the case of unexpected adverse events likely related to the intervention. If an unexpected adverse event or serious adverse event does occur, the investigator will consider whether corrective actions should be made to study procedures in order to protect the safety and welfare of study subjects. If any changes are made the Protocol and Informed Consent Form will be updated and these edits will be submitted as an Amendment to the IRB.

If a subject's clinical condition deteriorates substantially by self-report and clinician assessment, the subject will be withdrawn from the study. Subjects may also be withdrawn if the PI feels that the study poses a substantial risk to the participant or if the PI decides that a higher level of care is needed.

Procedures used in this study are consistent with safe and ethical research practices and do not unnecessarily expose subjects to risk. Adverse events are expected to be infrequent given the excellent safety profile of t-PBM, but should they arise, the PI will review the adverse event and report it to the IRB. Moreover, study staff and subjects may report concerns directly to the IRB.

Every effort will be made to enhance the comfort of subjects while throughout the study procedures. Subjects will be informed that they can stop any study procedure at any time if needed.

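### Participants who worsen or become actively suicidal are removed from the study, not only from t-PBM, and no safety follow-up is specified after exit

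*Combined protocol and SAP*

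**What the plan says.** Three rules end participation.

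- Section 7, on clinical decompensation, covers worsening that makes it unsafe to continue: "In such cases, the patient is immediately transferred to standard clinical treatment and exited from the research".
- Section 7, in the suicidality plan, covers specific ideation, intent or a plan, a positive answer to C-SSRS question 4 or 5, or any non-zero answer to PHQ-9 question 9. The instruction is: "then they will be proactively discontinued from the study and referred to adequate care". For milder ideation the response is instead that "the study team will respond with close monitoring of the subject".
- Section 10 covers substantial clinical deterioration: "the subject will be withdrawn from the study".

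Section 6 schedules two contacts after treatment. The first is a check-in: "A licensed study clinician will call the participant (phone or video call) approximately 2-3 days after the final treatment session". It includes adverse event (AE) review, C-SSRS and CGI-S/I. The second is an in-person visit about a week after the last session, which repeats those items and adds the SAFTEE, the symptom scales and the gambling tasks.

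On capture and reporting, the Adverse Events Form "captures any adverse event (serious or otherwise) that the subject experiences while participating in the study". Section 10 states that unanticipated problems "should be reported if they occur during the conduct of the study, after study completion, or after subject withdrawal or completion".

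**The concern.** A participant who becomes too unwell to continue should stop the intervention and receive care. Ending research contact at the same moment is a separate decision, and here it falls on the people whose safety course matters most.

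Three features of this trial sharpen the point. Section 7 asks participants to keep treatment unchanged, accepts that this may raise suicide risk, and offsets that risk partly by frequent contact with study clinicians. For those in whom the risk materialises, no further study contact is specified. Within the suicidality plan, the milder presentation is given monitoring by the study team, while the more serious one is given only discontinuation and referral. Finally, Section 9 aims at an initial safety profile in this population. With a target of 20 treated participants, each one is 1/20 = 5% of the group, so one event with an unknown outcome carries weight.

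**Working it through.** The plan gives no figure on this point, so the check sets its provisions side by side.

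**1. Does exit mean leaving the study or stopping t-PBM?** All three rules refer to the study or the research. The protocol does use a lower level of stopping elsewhere: in Section 10, discomfort that cannot be relieved stops only the application session. The wider wording for worsening is therefore best taken at face value.

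**2. Does any provision supply contact after exit?**

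- *Check-in call and follow-up visit (Section 6).* Both are timed from the last treatment session, not from Treatment 5, so they could apply to someone who stops early. Neither is said to be kept for a participant who has been removed.
- *Adverse Events Form (Section 6).* It defines which events are captured. It does not say how long a captured event is followed.
- *Reporting after withdrawal (Section 10).* This is a reporting duty for a narrow class of events. It plans no contact through which such events would become known.
- *Clinician availability (Section 10).* "Experienced, doctoral-level clinicians will be available to participants by phone, or in-person if necessary, to discuss any concerns throughout the study". This depends on the participant asking, and it is tied to the study period.
- *Stopping early (Section 5).* The stated provision is payment for procedures completed.

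None of these is an early-termination assessment or a plan to follow the triggering event.

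**3. What would be missing if exit ends contact?** From Section 6, the scheduled C-SSRS time points are screening, baseline, the call and the follow-up visit. CGI-S is rated at baseline, and CGI-S/I at the call and the follow-up visit. Each therefore has 2 scheduled post-baseline assessments.

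| Exit point | C-SSRS obtained | CGI-S/I obtained |
|---|---|---|
| Any time before the call | 0 of 2 | 0 of 2 |
| At the call, after its assessments | 1 of 2 | 1 of 2 |
| Any time, if call and visit still apply | up to 2 of 2 | up to 2 of 2 |

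The middle row can arise because the clinician may use the PHQ-9 at the call, and a non-zero answer to its question 9 triggers exit before the one-week visit. The counts are of scheduled assessments only. An unscheduled C-SSRS could be done when a concern arises, and a positive answer to question 4 or 5 is itself a trigger.

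**4. What is not lost?** AEs are actively reviewed at Treatments 2 to 5, and the TSRQ is completed after every session, so a good deal of safety information exists before exit. The triggering event occurs while the person is still a participant and falls within the AE Form. Aim 1 compares sham with active stimulation within the day-1 scan, before most exits could occur.

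**The case against.** The strongest reply is that this is an ambiguity and not a defect. On the timing wording the call and visit still apply, and the loss is then nil. Exit to clinical care is also a defensible protective choice for people who may be manic, psychotic or acutely suicidal and whose capacity to continue in research may be in doubt. Other safeguards exist: immediate transfer or referral, weekly safety review, reporting of unanticipated problems after withdrawal, and review of AEs by the investigator.

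Much of this stands. The alternative reading is possible, and any fix must be conditional on capacity and consent. But staff should not have to infer from timing wording whether to call a participant removed for suicidality, and none of the safeguards sets a follow-up contact.

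A reader might infer more than the documents support:

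- *That participants are abandoned.* They are not, since transfer or referral is stated. The gap is in the study's own follow-up and record of outcome.
- *That worsening between Treatments 1 and 5 would surface only by spontaneous report or clinical judgement.* AEs are reviewed at each of Treatments 2 to 5, and the SAFTEE and MOODS-SR are given at Treatment 5.
- *That the number of safety forms missed measures the loss.* Such a total depends on which forms are counted (whether the TSRQ is included, for example) and assumes that unwell participants complete every assessment offered. It does not measure clinical or inferential loss.
- *That the symptom-scale results are shown to be biased.* Section 9 plans a mixed model, which can use the available observations, and the Treatment 5 scales are listed ahead of the scan, so later exits have day-5 values. The model does not cure dropout caused by unobserved worsening. A favourable tilt is thus possible, but its size is unknown.

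**Conclusion.** The point holds. As written, the exit rules take participants with the most serious safety events out of the study, and nothing keeps the check-in call or one-week contact for them or provides for following the triggering event. If exit ends contact, a participant removed before the call has no scheduled post-baseline C-SSRS or CGI-S/I, and the outcome of the event may never reach the study. If the call and visit are meant to continue, nothing is lost and the change only makes that explicit.

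How many participants would be affected cannot be stated, because the documents give no expected withdrawal rate. The conclusion rests on the plain meaning of the exit wording. It does not extend to biased AE counts over treated participants or to harm to Aim 1. Possible favourable bias in the day-5 and follow-up symptom scales is a secondary, unquantified caveat to state when reporting.

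**What to change.** Keep all triggers and the immediate referral. In Sections 7 and 10, reword the three rules so that the participant discontinues t-PBM and is referred to care. Then add that, where the participant has capacity and has not withdrawn consent:

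- the clinician check-in call is kept, 2-3 days after the last session received, with AE form, C-SSRS and CGI-S/I;
- a brief safety contact takes place at about one week, allowed remotely, with AE form, C-SSRS, CGI-S/I and, if tolerable, the SAFTEE;
- the triggering AE is followed to resolution or to the end of that window.

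Report withdrawals for worsening over all treated participants, and state beside the symptom-scale results that values may be missing because participants worsened.

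The cost is protocol and consent wording, plus clinician time for one call and one short contact per affected participant. The call is already in the schedule. The one-week visit is currently in person, so the remote option is a small procedural change. The downside is some burden on a few unwell people, who may decline.
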